### 8.1.1 Patient identification

We will identify eligible patients through the CPOE. All patient data will be included for those patients for which the physicians ordered laboratory tests for one of the 17 study indications. The laboratories will log all the indications for which laboratory tests were ordered, and this will allow them to identify the patients for which we will extract laboratory and patient data. A member of the research team will confirm the eligibility of the patient data for inclusion in the trial.

Patient identification will be done using the pseudonymised national security number of the patient. All patients treated by the family physician for which the online CPOE was used to order laboratory tests will be included in the study without exclusions. Data from patients where the physicians used the paper-based order forms will not be included because the physicians do not document the indication for the laboratory tests in this situation. The pseudonymised national security number of patient can be de-encrypted allowing the study physicians to identify patients enrolled in the study while keeping the research facility blinded to their identity (see section 10 for a full description of the data collection).

### 8.1.2 Screening

In our study, no screening of patients for inclusion or exclusion will be necessary.

## 8.2 Consent

All enrolled physicians will be requested to provide a signed **clinical study agreement** before allocation. Participating physicians who fail or refuse to provide an informed consent will be excluded from the study.

All patients for whom a laboratory test order is made during the intervention period will be asked for consent to share their patient data with the research facility. We will use wording as in **Appendix 1.1** for consent.

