### 8.3.1 Method of implementing the allocation sequence

Randomization will be done using an electronic random numbers generator blinded to the research facility. The research facility will be kept blinded to the allocation, but collaborating laboratories will be able to identify intervention and control physicians. Allocation will be kept blinded to all study physicians until the start of the study. At the start of the study, physicians will be aware of the intervention and their allocation to either the intervention or control arm, however patients and research facility will be kept blinded to this allocation during the study and until after the data analysis.

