
Sample size for comparison of 2 proportions (binary values): 2-sided equality

Appropriateness: pA: 70%

Clinically significant change of 10% (to pB: 80%)

$\alpha = 0.05$

$1-\beta = 0.80$

$K = 1$

Sample size: 586

Sample size calculations based on Campbell et al (Campbell 2004) for a trial with 80% power to detect a difference of 10% (increase of appropriateness from 70% to 80%) with a significance of 10% predict 586 tests.

Design effect of clustering on sample size based on Teerenstra et al (Teerenstra 2008):

4 level setting comprising test, patient, physician and primary care practice:

1. Multiple study tests per patient, assumed to be 5 per patient,
2. Multiple patients per physicians, assumed to be 42 per 3 months if there is 70% use of the online intervention and 1/3 indications included in the study,
3. Multiple physicians per primary care practice (PCP), assumed to be 2.35 based on preliminary data by Heselmans et al. (Heselmans 2013)

We assume an intracluster coefficient of 0.2 for each level of clustering.

$Rho_n$  = correlation between two physicians active in the same PCP

$Rho_s$  = correlation between two patients cared for by the same physician

$Rho_e$  = correlation between two tests ordered for the same patient

$n_n$  = mean amount of physicians per PCP

$n_s$  = mean amount of patients per physician

$n_e$  = mean amount of study tests per patient

$Phi_e = 1 + Rho_e * (n_e - 1)$

$Phi_s = 1 + Rho_s * (n_s - 1) * w_e$

$Phi_n = 1 + Rho_n * (n_n - 1) * w_n$

$w_e = (n_e * Rho_e) / (1 + Rho_e * (n_e - 1))$

$w_s = (n_s * Rho_s) / (1 + Rho_s * (n_s - 1))$

The final design effect (DE) =  $Phi_e * Phi_s * Phi_n$

Applied to our protocol:

$n_n$  = mean amount of physicians per PCP = 2.35

$n_s$  = mean amount of patients per physician = 42 per 3 months

$n_e$  = mean amount of study tests per patient = 5

$Phi_e = 1 + Rho_e * (n_e - 1) = 1.8$

$Phi_s = 1 + Rho_s * (n_s - 1) * w_e = 5.56$

$Phi_n = 1 + Rho_n * (n_n - 1) * w_n = 1.25$

$w_e = (n_e * Rho_e) / (1 + Rho_e * (n_e - 1)) = 0.56$

$w_s = (n_s * Rho_s) / (1 + Rho_s * (n_s - 1)) = 0.913$

The final design effect (DE) =  $Phi_e * Phi_s * Phi_n = 1.8 * 5.56 * 1.25 = 12.465$

586 test \* 12.465 (DE) = 7305 test = 1460 patients = 35 physicians during 3 months

Figure 15: Sample size calculations for primary outcome appropriateness including inflation due to multi-level clustering

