## 12 ETHICAL AND REGULATORY CONSIDERATIONS

### 12.1 Research Ethics Committee (REC) review & reports

The study will be conducted in compliance with the principles of the Declaration of Helsinki (current version), the principles of GCP and in accordance with all applicable regulatory requirements. Before the start of the study, this protocol, the informed consent forms and other related documents e.g. advertisements and GP information letters, will be submitted for review to the REC and to the Sector Committee for Social Security and Health of the Privacy Commission. The study shall not commence until such approvals have been obtained.

Any subsequent protocol amendments will be submitted to the REC and Sector Committee for approval. No substantial amendment that require review by REC will be implemented until the REC grants a favourable opinion for the study.

The study can and will be conducted only on the basis of prior informed consent by the study participants, or their legal representatives, to participate in the study. Extensive discussion of risks and possible benefits of participation will be provided to the patients and/or their families. The participating physician shall obtain a signed informed consent form for all study participants prior to their enrolment and participation in the study in compliance with all applicable laws, regulations and the approval of the (local) Ethics Committee, if required. The research facility shall retain such ICFs in accordance with the requirements of all applicable regulatory agencies and laws.

All correspondence with the REC shall be retained in the Trial Master File/Investigator Site File.

The Chief Investigator acknowledges that it is his responsibility to produce annual progress reports (APR) and he will do so by submitting to the REC within 30 days of the anniversary date on which the favourable opinion was given, and annually until the study is declared ended.

The Chief Investigator shall notify the REC of the end of the study. Should the study be ended prematurely, the Chief Investigator will notify the REC and include the reasons for the premature termination. The Chief Investigator will submit a final report with the results, including any publications/abstracts, to the REC.

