3.3. Sample size

For sample size calculations, we refer to the protocol and appendix 3 of the protocol. At the end of the six-month intervention period the planned sample size was verified based on the number of recruited physicians and the average number of patients per physician. With 280 study physicians (clusters), a sample of 12740 patients (45.5 patients on average per physician) would be necessary to have at least 80% power for the secondary outcome (diagnostic error), assuming the original intra-cluster correlation and diagnostic error rates. At that point we had recruited 11200 patients and it was deemed unfeasible to recruit an additional 1500 patients. Since most recruitments were realised by physicians who had already recruited 50 or more patients, the Steering Committee agreed that attempts to recruit additional patients should target physicians with a low number of recruited patients. Therefore, only those physicians who had not yet recruited 10 patients were allowed another month to recruit additional patients. Specific calculations regarding the sample size and the assumed intra-cluster correlations can be found in the protocol under 9.1.

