4. KCELABGP_COM

6.1.1.KCELABGP_LAB

The KCELABGP_LAB database contains the data collected through the ambulatory laboratories. This database contains several tables, each containing data from the same data collections. The tables included in the KCELABGP_LAB database are TU_KCELABGP_LAB, TU_KCELABGP_LAB_INDICATN, TU_KCELABGP_LAB_TST, TU_KCELABGP_LAB_ORD_SETS, TU_KCELABGP_LAB2 and TU_KCELABGP_LAB2_LAB_TST.

TU_KCELABGP_LAB

This table contains data on each individual laboratory panel linked to an individual patient. The table includes information on date of birth, sex, reimbursement codes, physician, date of the laboratory test

panel, date of death (if applicable) and total cost of the laboratory test panel. Each row in this table represents a unique laboratory test panel and a single patient may be represented more than once.

TU_KCELABGP_LAB_INDICATN

This table contains data on the indications for each laboratory test panel. It includes data on the selected indications and the additional information provided by the physician when code 99 was used. Code 99 implied that the physicians reported that an indication was applicable outside of the 17 study indications. The exact nature of this indication was included in a free text field of the CPOE. Each row represents a unique indication. Since many laboratory test panels had more than one indication, most panels are represented multiple times.

TU_KCELABGP_LAB_LAB_TST

This table contains data on all ordered laboratory tests. Data on the laboratory test (either a Logical Observation Identifiers Name and Codes (LOINC) code or a Medidoc code), result of the test, upper limit, lower limit are included. Data on whether the result represents a normal or abnormal value is also included. The laboratory test results can be numeric or alphanumeric so that a wide variety of results are possible. Each row in the table represents a unique test. Each panel is represented multiple times as is each patient.

TU_KCELABGP_LAB_ORD_SETS

This table contains data on the selected order sets. For each possible indication, multiple order sets were developed. For instance, for the indication 'hypertension' an order set was developed for the diagnosis of hypertension, for the follow-up of hypertension and so on. This table includes more detailed information on the exact order set that was selected with respect to the indication.

TU_KCELABGP_LAB2 and TU_KCELABGP_LAB2_LAB_TST

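### Patients entered by consent taken after allocation by physicians who knew their arm, yet no outcome model uses patient age or sex and nothing compares included with eligible patients

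*Protocol*

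**What the plan says.** **Entry of patients.** Protocol 8.2 names the group to be approached as "All patients for whom a laboratory test order is made during the intervention period", and they "will be asked for consent to share their patient data with the research facility". Protocol 12.1 states who does this: "The participating physician shall obtain a signed informed consent form for all study participants prior to their enrolment". Protocol 8.3.1 says that once the study starts, "physicians will be aware of the intervention and their allocation to either the intervention or control arm". The intention was complete entry: under Protocol 8.1.1, patients with an online order "will be included in the study without exclusions", and 8.1.2 foresees no screening.

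**What happened.** SAP 3.1 gives a six-month intervention period and SAP 3.2 gives 280 physicians in 72 practices. SAP 3.3 reports, for the end of that period, "At that point we had recruited 11200 patients". It adds that most entries came from physicians who already had 50 or more patients. Physicians with fewer than 10 were given one more month.

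**Checks and models.** SAP 5 judges completeness of data collection against the number of signed consent forms, and the report in SAP 7.1 lists missing forms by physician, laboratory and record system. The GEE models in SAP 10.2.1 and 10.2.2 contain allocated group and laboratory, with practice as the cluster. Protocol 9.3.1 compares patient characteristics between arms. Protocol 9.5 plans adjusted analyses using prior test volume, number of patients in the practice, and physician age or years worked.

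**Data held.** For the laboratory panel table in SAP 6.1.1, "The table includes information on date of birth, sex, reimbursement codes, physician". SAP 6.4.1 keeps patient age as a continuous variable because it matters for later analyses, but no model names it.

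**The concern.** Randomising practices balances practices and the patients who attend them. It does not balance the patients who are entered, if entry depends on a later decision by someone who knows the arm. Here the physician obtains the consent after allocation, and the two arms work differently at the moment of ordering: one sees preselected tests and the other an empty form. If that difference, or knowledge of the arm, changes which patients are asked or agree, the included patients differ between arms for reasons unrelated to the effect of the order sets.

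Both main contrasts are exposed. Appropriateness is a proportion per patient and may depend on the kind of patient. Diagnostic error is judged against a margin of 1 percentage point on an assumed rate of 2.5%, so a modest difference in patient risk could matter. The plan should therefore show who was not entered, and use the patient variables that allocation cannot affect.

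**Working it through.** **1. The plan's own figures.** Inputs (Protocol 9.1.2): rate 2.5% in both arms, margin 1%, power 80%, significance 5% (which reproduces as one-sided), intracluster correlation 0.025.

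- Per arm: (1.645 + 0.842)² × 2 × 0.025 × 0.975 / 0.01² = 3,014, so 6,028 in total (stated 6,032).
- Three months: 6,032 × 2.025 / 42 = 290.8 physicians (stated 290). Six months: 6,032 × 3.075 / 84 = 220.8 (stated 220).
- SAP 3.3 with 280 physicians: solve 280m = 6,032 × [1 + 0.025(m − 1)]. Then m = 5,881.2 / 129.2 = 45.52 and 280 × 45.52 = 12,746 (stated 12,740, from 45.5 per physician).

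The stated sample sizes reproduce, so the assumed patient flow can be taken at face value as the planning figure.

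**2. Assumed flow.** Protocol Figure 15 gives patients per physician as "assumed to be 42 per 3 months if there is 70% use of the online intervention and 1/3 indications included in the study". With 15 patients a week (Protocol 9.1): 15 × 12 × 0.70 / 3 = 42. The figure is therefore already net of paper orders and of non-study indications. Protocol 9.1.2 uses 84 for six months. (Protocol 9.2 describes the 15 a week as already limited to study indications. Without the one third the product would be 126 per three months. I keep the 42 that the protocol carries through its calculations.)

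**3. Entry against that flow.** 280 × 84 = 23,520. 11,200 / 23,520 = 47.6%, or 11,200 / 280 = 40 per physician against 84.

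**4. Other denominators.**

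- Recruited physicians including the 8 early drop-outs: 288 × 84 = 24,192, giving 46.3%.
- Re-checked target: 11,200 / 12,740 = 87.9%.
- Original plan: 300 × 42 = 12,600, giving 88.9%.

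The first kind of denominator, expected flow, is the relevant one for asking who was left out. The second kind describes progress towards the sample size.

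**5. What the plan can and cannot show.**

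- Imbalance among included patients: visible through Protocol 9.3.1.
- Differences between practices or physicians: addressed in part by Protocol 9.5.
- Patients eligible but not entered: not visible, because the reference count in SAP 5 is signed consent forms.
- Patient-level baseline adjustment: none. The per-indication analysis in SAP 10.2.1 adds the number of additional indications. That is recorded for the panel, after allocation, by a physician who knows the arm, so it is not a baseline variable.

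**The case against.** **The shortfall is not evidence of selection by arm.** A reader might infer from 47.6% that physicians picked their patients differently in the two arms. The documents do not support this. The count is pooled over arms, and no count of eligible, approached or refusing patients is given. The 84 is a planning assumption that also equates one panel with one patient, whereas SAP 6.1.1 allows several panels per patient. Lower use of online ordering, less ordering or repeat panels could each explain part of the gap, and 11,200 is the count before the extra month. All of this stands.

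**The plan is not blind.** A reader might also infer that it has no means of seeing or reducing selection. That goes too far. Protocol 9.3.1 would reveal imbalance in the patient characteristics compared, among those entered, and Protocol 9.5 adjusts for physician and practice variables. The SAP presents itself as an elaboration of the protocol's plan, so these analyses are not shown to be withdrawn. Neither reaches patients who were never entered, and neither puts a patient variable in an outcome model.

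**The remedy is partial.** Age and sex may be only weakly related to who is entered or to the outcomes. This also stands. It limits what the adjustment can be claimed to do, but is not a reason to leave out two variables that allocation cannot affect.

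**Conclusion.** The mechanism for selective entry is documented: consent after allocation, obtained by physicians who knew their arm, with very uneven entry. Differential selection is a risk. The documents do not show that it occurred, or in which direction.

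Its size cannot be derived from the documents. Protocol 5.2 reports 38% to 60% inappropriate tests across five indications, and it is tempting to turn that 22-point spread into a bias in the primary contrast. That would need an assumed shift in mix between arms. The spread is also between indications, and nothing links it to age or sex, so it does not measure what the adjustment below would remove.

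Two gaps remain. No comparison of included with eligible patients is planned, and no outcome model uses a patient-level baseline variable even though SAP 6.4.1 calls age important. The conclusion rests on the consent procedure having run as Protocol 8.2 and 12.1 describe, and on age and sex being sufficiently complete; SAP 6.1.1 lists the fields but does not state completeness.

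**What to change.** 1. Before unblinding, add patient age (continuous, with its form fixed in advance) and sex to the GEE models for appropriateness in SAP 10.2.1 and diagnostic error in SAP 10.2.2. If unblinding has already occurred, specify this as an adjusted sensitivity analysis and label it so.
2. Report standardised marginal proportions per arm and their difference. Take the standard error of the difference from the model's robust covariance by the delta method. The rule in SAP 10.2.2 for two independent estimates would not apply, because the two standardised proportions share the covariate coefficients.
3. Where the laboratory logs allow, report by arm, for each physician, the number of included patients over the number of eligible online-order patients. Protocol 8.1.1 says the laboratories log the indications, and Protocol 9.8 makes an indication compulsory for validating an order, so the denominator should be obtainable as a count without patient data.

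**Cost.** Slightly more analysis work, two variables from a table already held, and a count per physician from the three laboratories. The model can carry the extra terms: at the protocol's assumed rate, 11,200 × 0.025 = 280 patients would have a missed diagnosis. The adjustment removes only selection related to age and sex; the included-over-eligible report is what would show whether entry differed by arm.

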## 8.3 The randomisation scheme

PCP's will be randomized to either the intervention or control arm after stratification based on their experience in the use of a CPOE. We suspect that previous experience in using a CPOE will influence the effectiveness of order sets. Hence we will stratify all PCPs according to the self-reported experience in the use of a CPOE by its physicians. A random numbers generator will be used to randomise enrolled physicians. The research facility will be blinded to the randomization.

### 8.3.1 Method of implementing the allocation sequence

Randomization will be done using an electronic random numbers generator blinded to the research facility. The research facility will be kept blinded to the allocation, but collaborating laboratories will be able to identify intervention and control physicians. Allocation will be kept blinded to all study physicians until the start of the study. At the start of the study, physicians will be aware of the intervention and their allocation to either the intervention or control arm, however patients and research facility will be kept blinded to this allocation during the study and until after the data analysis.

## 8.4 Blinding

The research facility will be kept blinded to the allocation during the whole study until after data analysis. The collaborating laboratories will be aware of the allocation as they will need to implement the intervention. Participating physicians will be kept blinded to their allocation until the start of the study, however patients will be kept blinded.

## 8.5 Un-blinding

Conditions and procedures for un-blinding are not required as participating physicians will be aware of their allocation. We do not foresee any reasons (such as severe adverse events) requiring the un-blinding of the research facility. Physicians are not required to adhere to the advice of the order sets and all diagnostic decisions remain the responsibility of the ordering physician.

## 8.6 Baseline data

Baseline data to compare participating physicians will be obtained at the start of the study. This data includes:

- Size of the PCP (how many active physicians)
- Age of the participating physician at the start of the study
- Sex of the participating physician
- Number of active years in general practice of the participating physician at the start of the study
- Average number of tests per laboratory order in the three months prior to the study, as a measure of baseline testing volume
- Experience in the use of a CPOE prior to the study

## 8.7 Trial assessments

Month 0-9:

Information on the barriers and facilitators to the use of a CPOE and order sets will be obtained through interviews with participating physicians, clinical biologists and information technologists. With the GUIDES instrument (Van [name] 2016) as guide, we will involve a purposive sample of each of these stakeholders and tailor the order sets to maximise user-friendliness and effectiveness. Differences in the implementation of the CPOE and the order sets over the laboratories will be inventoried and used to compare effectiveness. See 8.9.1 for more detail.

#### **Month 6-9:**

Information on usability of the study intervention, extracting required data, obtaining patient consent and usability of HD4DP for documenting secondary outcome measures.

#### **Month 12:**

After the intervention period of three months the following data will be provided to the research facility by the collaborating laboratories:

- For each of the 17 study indications, name and value of all tests ordered using the CPOE;
- The total volume of tests for all indications;
- The number of paper-based orders being performed alongside the CPOE and the total volume of tests this comprises.

## **8.8 Long term follow-up assessments**

#### **Month 9-18:**

For all patients included in the trial, their physician will be requested to document all diagnoses made in his patient in the six months following the laboratory test (irrespective of possible diagnostic error). For all patients in which the physician documented a potentially missed diagnosis, a review of data extracted from the EHR will be performed by one of the researchers blinded to the allocation, to confirm that the potentially missed diagnosis is truly related to the initial laboratory test. He will document his evaluation and a second reviewers will validate his response. In case of disagreement a senior researcher will be consulted. Additionally, the patient will be interviewed by telephone to detect any additional cases of diagnostic error. A sample of patients for which no apparent diagnostic error occurred will also be interviewed by telephone to confirm the absence of diagnostic error.

